5.6 Prior and Concomitant Therapy

Patients' concomitant medical therapies and recently completed (within the past three months) medical therapies will be recorded. All patients are required to have received oral corticosteroids to determine eligibility for enrollment. Most concomitant therapies are permissible. Medications that are contraindicated during treatment are TNF antagonists and chemotherapies.

5.7 Packaging

Anakinra will be supplied in single use, pre-filled glass syringes in a 4x7 dispensing pack of 28 syringes (one box). Each syringe contains 100mg of Anakinra. Each box should last 28 days.

5.8 Blinding of Study Drug

Not applicable.

5.9 Receiving, Storage, Dispensing and Return

5.9.1 Receipt of Drug Supplies

Upon receipt of the of the study treatment supplies, an inventory must be performed and a drug receipt log filled out and signed by the person accepting the shipment. It is important that the designated study staff counts and verifies that the shipment contains all the items noted in the shipment inventory. Any damaged or unusable study drug in a given shipment will be documented in the study files. The investigator must notify study sponsor of any damaged or unusable study treatments that were supplied to the investigator's site.

5.9.2 Storage

Anakinra should be stored in the refrigerator (36 to 46 degrees F). The drug should not be frozen or shaken. Furthermore, it should be protected from light.

5.9.3 Dispensing of Study Drug

Anakinra will be dispensed to enrolled patients by providing them with a 28 day supply and a sharps container for used syringes. The patient will complete daily logs of drug administration. Upon the completion of the 28 day course, the patient will return to the office with the filled sharps container and any unused medication. This reconciliation process will be completed before providing the patient with the next 28-day course of medication.

5.9.4 Return or Destruction of Study Drug

At the completion of the study, there will be a final reconciliation of drug shipped, drug consumed, and drug remaining. This reconciliation will be logged on the drug reconciliation form, signed and dated. Any discrepancies noted will be investigated, resolved, and documented prior to return or destruction of unused study drug. Drug destroyed on site will be documented in the study files.

6 Study Procedures

All patients will initially be treated with a 30-day course of corticosteroids. Only those patients that failed to respond to corticosteroids (as defined in section 3.1) will be approached to enroll in this clinical trial. The option to undergo treatment with Anakinra for a corticosteroid resistant hearing loss will be explained to the patient. The sponsor-investigator, [name], has a Conflict of Interest (COI) and will not directly consent patients from her practice. The nature of the conflict is that she and the Feinstein Institute hold a use patent for interleukin-1 antagonist therapy for autoimmune and sudden hearing loss as well as Meniere's disease. This conflict will be disclosed to all patients considering participation in this study. Any patients designated appropriate for study by the inclusion/exclusion criteria will be consented by her partner, [name], who does not have a COI. The other study investigators ([name] and [name]) have no COI and therefore will be able to consent patients from their own practices. Risks and potential benefits of anakinra therapy will be described.

6.1 Visit 1(Baseline)

Once the corticosteroid resistant patient has been identified at the end of a 28-30 day course of oral corticosteroids, enrolled patients will undergo blood testing (If the patient underwent a CBC, SMA-7 within 2 weeks prior to visit 1, those bloods will be accepted as enrollment criteria bloodwork). The audiogram taken at the end of the corticosteroid treatment will be used as the time 0 audiogram. Throughout the study, the audiologists will be blinded to the study treatment timepoint. Blood will be taken for a CBC, SMA-7, serum HCG or UCG (if female of childbearing age) and plasma IL-1 β and studies for IL-1 β stimulation in PBMC (30cc). The labs will be checked: if there is no evidence of neutropenia, renal insufficiency or pregnancy, the patient will be asked to meet with study nurses for instruction for self administration of anakinra. The patient will be asked to maintain a daily log of injections, injection site reactions and any associated symptoms (fluctuating hearing, vertigo, tinnitus, headaches).

6.2 Visit 2

At 28 days post-initial Anakinra treatment the patient will return for repeat audiometric testing and provide a blood sample (30cc). The daily logs would be reviewed by the study nurses weekly. The logs would be reviewed by the clinician at the time of the visit. Injection sites would be inspected and reactions documented. The blood specimen would be used to determine the CBC with differential, SMA-7, serum HCG (for females of child-bearing age) and IL-1 β plasma level and induction. The patient would be instructed to bring any remaining drug to the visit (if possible) as well as the spent syringes in the sharps container. The patient would be given a new 28 day supply of Anakinra and a new sharps container. CBC and SMA-7 results would be reviewed within 72 hours and any patients with changes in their white blood cell numbers, neutrophils numbers or creatinine values will be contacted. Any patient that develops neutropenia or renal insufficiency will be excluded from receiving further drug.

6.3 Visit 3

At 56 days post-initial Anakinra treatment the patient will return for repeat audiometric testing and provide a blood sample (30cc). The daily logs would be reviewed by the study nurses weekly. The logs would be reviewed by the clinician at the time of the visit. Injection sites would be inspected and reactions documented. The blood specimen would be used to determine the CBC with differential, SMA-7, beta HCG and IL-1 β plasma level and induction. The patient would be instructed to bring any remaining drug to the visit as well as the spent syringes in the sharps container. The patient would be given a new 28 day supply of Anakinra and a new sharps container. CBC and SMA-7 results would be reviewed within 72 hours and any patients with changes in their white blood cell numbers, neutrophils numbers or creatinine values will be contacted. Any patient that develops neutropenia or renal insufficiency will be excluded from receiving further drug.

6.4 Visit 4

At 84 days post-initial treatment the patient will return for repeat audiometric testing and provide a blood sample (30cc). The daily logs would be reviewed by the study nurses weekly. The logs would be reviewed by the clinician at the time of the visit. Injection sites would be inspected and reactions documented. The blood specimen would be used to determine the CBC with differential, SMA-7, and IL-1 β plasma level and induction. The patient would be instructed to bring any remaining drug to the visit as well as the spent syringes in the sharps container. CBC and SMA-7 results would be reviewed within 72 hours and any patients with changes in their white blood cell numbers, neutrophils numbers or creatinine values will be contacted.

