- **Definition of corticosteroid non-responder**: All patients must have been treated with 60mg of oral prednisone for a minimum of 7 days with a variable taper thereafter, for a minimum of 30 days in total, and response to prednisone therapy measured by audiometry before treatment and at approximately 30 days post-treatment. Audiometry will consist of a pure tone average ((PTA): here to include 250, 500, 1000, 2000, and 4000Hz) and speech discrimination score to be recorded pre and post treatment. Clinical responsiveness will be defined as either an average of 5 decibel or greater PTA improvement (as the average of five frequencies was recorded) in their post-treatment audiogram, or a greater than 12% improvement in the speech discrimination scores. In the event a patient with a pre-treatment profound SNHL demonstrates an improvement on PTA, however, no improvement in speech discrimination is noted, and the initial speech discrimination is 0%, this patient would be classified as a non-responder. Patients that received concurrent or sequential intratympanic corticosteroids may be included only if they received the 30 days of oral steroids as well.
- *Entrance into the research protocol:* Patients that failed to respond to corticosteroid therapy will be offered anakinra therapy as an alternate therapy to continued corticosteroid therapy. Given that anakinra is a daily subcutaneous injectable, it is unethical to perform a placebo controlled trial where a patient potentially could receive 84 consecutive days of injectable saline. Moreover, the total projected number of patients for this phase I/II trial is too low to consider a cross-over design. Thus an open-label trial design is proposed. Patients will be monitored every 28 days while on therapy

by audiogram and laboratory values. Laboratory values include a Complete Blood Count (CBC) with differential, SMA-7, HCG or UCG (for child-bearing aged females) and plasma IL-1 β levels/stimulation studies. Patients will complete daily logs as to injection site reactions and other potential side effects.

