4.1 Inclusion Criteria

1. Patients must have Autoimmune Inner Ear Disease, Meniere's Disease, or Sudden Sensorineural Hearing Loss with autoimmune features.

CONFIDENTIAL This material is the property of the Feinstein Institute for Medical Research, North-Shore-LIJ Health System. Do not disclose or use except as authorized in writing by the study sponsor

- 2. Age and Gender: males and females ages 13 to 75 weighing 90 lbs or greater will be recruited.
- 3. Patients must be capable of understanding and giving informed consent.
- 4. If the recruited patient is between the ages of 13 and 17, an assent will be obtained from the patient and consent from one parent/legal guardian prior to enrollment.
- 5. Patients must have SNHL of greater than 30dB at one or more frequencies in one or both ears with evidence of active deterioration (elevated threshold) in at least one ear of 15 dB at one frequency (excluding 250 or 8kHz as a sole indicator) on their audiogram, or 10dB at 2+ frequencies developing in >3 days but <90 days, or in the case of SSNHL, the hearing loss may evolve in less than 3 days if the patient displays features suggestive of an autoimmune disorder.
- 6. Patients must have previously undergone a trial of high-dose corticosteroid therapy, at 60 mg daily for a minimum of seven days, with a variable taper thereafter that consists of a total of 30 consecutive days of corticosteroid use. Patients must have demonstrated less than or equal to a 5 decibel average improvement in their PTA in response to corticosteroids as measured by their audiogram.
- 7. Patients may have a concurrent other autoimmune disease(s).

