4.3 Subject Recruitment and Screening

Subjects will be recruited from the practices of several Neurotologists and Otolaryngologists from the North Shore-LIJ Health System. No recruitment materials will be disseminated; however, patients within these practices with a diagnosis of AIED, SSNHL or Meniere's Disease may be sent letters informing them of this clinical trial. All patients that are treated with corticosteroids (60mg per day for 7 days with a taper thereafter to 30 days of treatment in total) will be informed of the study availability to them only if they fail to respond to corticosteroids as measured on the audiogram at approximate 30 day post-treatment interval. The study will be described to the patient. Pre-treatment laboratory tests will be performed for inclusion (CBC, SMA-7, beta HCG or UCG (if female of child-bearing age)) at visit 1 (or within 2 weeks prior). Plasma IL-1 β and in vitro expression of IL-1 β in PBMC and monocytes will also be measured. Patients that fail corticosteroid therapy and meet inclusion and exclusion criteria will be given the option of enrolling in this phase I/II trial and receiving Anakinra. Alternatively, they may opt to receive continued corticosteroids, or no further treatment. It is possible that a number of patients will not wish to perform daily injections for 84 days.

Some patients that failed corticosteroid therapy (as measured by a pre and post treatment audiogram) may be referred by non-study physicians for participation in this study. Inclusion of these patients may be considered if no greater than 30 days has elapsed since the discontinuation of corticosteroids, and that the patient received 30 days of prednisone. In the event the patient did not receive 30 days of prednisone, the patient will be treated again with 60mg of prednisone for 7 days and a variable taper to achieve 30 days of continuous therapy. Audiometry will be repeated again at the end of the treatment. If the patient is still a "non-responder", they will have the option to enroll in this study.

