5.3 Method for Assigning Subjects to Treatment Groups

This open-label trial of Anakinra will not be randomized. Given the route of drug delivery, a placebo-controlled trial is not possible. All patients that fail corticosteroid therapy will be offered Anakinra, thereby avoiding selection bias for certain patients. All enrolled patients on Anakinra will undergo audiometric testing and blood collection at 0, 28, 56 and 84 days during the treatment period. Upon cessation of treatment, audiometric testing will again be performed at +30, +90 days and +180 days. During the same visit as audiometric testing, blood will be collected for a CBC, SMA-7, and IL-1 β plasma and stimulation studies.

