7.1 Sample Size Determination & Statistical Methods

Corticosteroid resistant AIED patients currently have no therapeutic alternatives available to them. These patients that failed initial corticosteroid therapy are not expected to demonstrate a placebo effect, as they have already undergone 2 serial audiograms that demonstrated a <5dB PTA improvement in hearing for trial inclusion. A Simon 2-stage "optimal" design will be used to test the null hypothesis that the true objective response rate (RR) is 10% or less (which would not be clinically meaningful) versus the alternative hypothesis that the true response rate is 30% or greater. With a significance level of 0.05 and a power of 0.80, a maximum total of 29 evaluable patients will be required to assess the objective response rate. Ten (10) evaluable patients will be enrolled in Stage 1(R21 phase). If 1 or fewer objective responses are observed in the first 10 evaluable patients, then the trial will be terminated (do not proceed to R33). Primary milestone: If 2 or more objective responses (improvement in the PTA \geq 5dB) are observed in the first 10 patients (20%), we will proceed to the R33 phase.

If the RR is 10% or less, then the expected sample size for the trial is 15 patients and the probability of early termination at the end of the R21 phase (stage 1) is 74%. Overall, a total of approximately 38 patients may be enrolled in this R21/R33 study to ensure that the specified numbers of evaluable patients are available for analysis at each stage.

Given that anakinra may cause injection site reactions, it is possible that some patients will prematurely self-terminate the study. In order to appropriately evaluate the results, 29 patients would need to complete the 84-day course of anakinra. Overall, a total of 38 patients may be enrolled in this study to ensure that the specified numbers of evaluable patients are available for analysis at each stage.

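### Section 6.1 reuses the audiogram that selected patients for not improving on steroids as the time-0 baseline, which adds a modest spurious gain to the 5 dB response

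*Protocol*

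**What the plan says.** On the baseline, Protocol section 6.1 states: "The audiogram taken at the end of the corticosteroid treatment will be used as the time 0 audiogram".

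On selection, section 4.1 item 6 uses the steroid course to qualify patients: "Patients must have demonstrated less than or equal to a 5 decibel average improvement in their PTA". Section 3.1 has "response to prednisone therapy measured by audiometry before treatment and at approximately 30 days post-treatment" and counts a gain of 5 dB or more as a steroid response. The second of these two audiograms is the one that section 6.1 makes time 0.

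The primary endpoint (section 3.2) compares hearing after 84 days of anakinra with the threshold before anakinra. Section 7.1 counts a PTA gain of at least 5 dB as an objective response. The trial has one arm.

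Section 7.1 also argues that these patients are "not expected to demonstrate a placebo effect, as they have already undergone 2 serial audiograms" showing less than 5 dB of improvement.

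On timing, section 5.3 says that patients "will undergo audiometric testing and blood collection at 0, 28, 56 and 84 days during the treatment period". For patients referred by non-study physicians, section 4.3 says: "Inclusion of these patients may be considered if no greater than 30 days has elapsed since the discontinuation of corticosteroids". It asks for repeat audiometry only when such a patient had not had 30 days of prednisone and is treated again. Screening bloods have a window in section 6.1 ("If the patient underwent a CBC, SMA-7 within 2 weeks prior to visit 1, those bloods will be accepted"). The audiogram has none.

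**The concern.** A patient enters because the end-of-steroid PTA is not at least 5 dB better than the pre-steroid PTA. Each PTA carries measurement error. Among patients who pass this one-sided filter, end-of-steroid readings that came out too poor by chance are over-represented. When that reading is also the reference for the day-84 change, the chance error tends to disappear at day 84 and is counted as gain.

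Two things are at stake. The response rate is tested against a fixed 10% null with no concurrent control, so any gain that is not due to the drug goes straight into the result. And section 7.1 uses the two audiograms as the reason not to expect improvement without drug, although selecting on them and then reusing the second has the opposite effect.

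**Working it through.** **1. The plan's own figures.** Section 7.1 gives p0 = 10%, p1 = 30%, alpha 0.05, power 0.80, 10 patients in stage 1 (stop at 1 or fewer responses) and 29 in all. The final cut-off is not stated. A search for the Simon optimal design gives more than 5 of 29, and that is used here.

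- Early stopping at p = 0.10: 0.9^10 + 10 × 0.1 × 0.9^9 = 0.349 + 0.387 = 0.736 (protocol: 74%).
- Expected N: 10 + (1 − 0.736) × 19 = 15.0 (protocol: 15).
- P(positive trial | p) = Σ over x = 2 to 10 of Bin(x; 10, p) × P(Bin(19, p) ≥ 6 − x). This is 0.047 at p = 0.10 and 0.805 at p = 0.30.

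The stated design reproduces and is not in dispute.

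**2. Model for an inert drug, one ear, PTA only.** A higher PTA is worse. Let d be the true improvement on steroids and s the error SD of one PTA; the errors e1 to e4 are independent Normal(0, s).

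- Pre-steroid PTA: T + e1. End-of-steroid: T − d + e2. Day 84: T − d + e3. Fresh day-0: T − d + e4.
- Eligible if d + e1 − e2 < 5.
- Response with the reused baseline: e2 − e3 ≥ 5. With a fresh baseline: e4 − e3 ≥ 5.

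The protocol gives neither s nor the distribution of d. Both are assumptions.

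**3. Formulas.**

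- Fresh: P = 1 − Φ(5 / (s√2)). At s = 3: 1 − Φ(1.179) = 11.9%.
- Reused, with d ~ Normal(m, τ): P = ∫ f(e) Φ((5 − m + e)/√(τ² + s²)) Φ((e − 5)/s) de, divided by ∫ f(e) Φ((5 − m + e)/√(τ² + s²)) de, where f is the Normal(0, s) density. Stable hearing is m = τ = 0.

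**4. Results, stable hearing.** Each rate is put into the step 1 formula.

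| s (dB) | Mean spurious gain, reused (dB) | False response, reused | False response, fresh | P(positive trial), reused | P(positive trial), fresh |
|---|---|---|---|---|---|
| 2 | 0.12 | 4.0% | 3.9% | 0.001 | 0.001 |
| 2.5 | 0.28 | 8.5% | 7.9% | 0.024 | 0.017 |
| 3 | 0.48 | 13.4% | 11.9% | 0.14 | 0.093 |
| 4 | 0.94 | 22.4% | 18.8% | 0.54 | 0.38 |

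With a fresh baseline the mean spurious gain is 0. Before rounding, the part due to reuse is 0.2, 0.6, 1.5 and 3.5 percentage points.

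**5. True steroid change varies between patients (assumed mean 5, SD 8 dB).** The filter then removes about half the patients and the excess grows. The fresh column of step 4 is unchanged.

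| s (dB) | Mean spurious gain, reused (dB) | False response, reused | P(positive trial), reused |
|---|---|---|---|
| 2 | 0.38 | 5.0% | 0.002 |
| 2.5 | 0.57 | 10.2% | 0.051 |
| 3 | 0.79 | 15.6% | 0.23 |
| 4 | 1.30 | 25.1% | 0.65 |

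**6. Age of the baseline.** Keep the step 5 assumptions with s = 3 and add a true shift between the old audiogram and the first dose. With 3 dB of further loss, false response is 4.2%; with no shift, 15.6%; with 3 dB of natural recovery, 38.6%. A 1 dB loss gives a mean net gain of 0.79 − 1 = −0.2 dB, which slightly more than cancels the selection effect.

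**The case against.** The strongest reply is that the effect of reuse is small and may be absorbed. A five-frequency average tends to be less noisy than a single threshold. If the error SD of one PTA is 2 dB or less, the 10% null covers the spurious responses and the chance of a positive trial for an inert drug stays far below 0.05. At 2.5 dB with stable hearing it is still 0.024. This stands: the documents do not show that the trial's error rate is broken.

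A reader might take the whole false-response rate at 3 or 4 dB as the cost of reuse. It is not. A fresh baseline still gives 11.9% and 18.8%, and 0.093 and 0.38 for a positive trial, because a 5 dB cut-off is close to the measurement noise at those SDs. Only the difference between the columns belongs to this point.

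A reader might also infer that an old baseline itself builds in improvement. The documents do not support that. Entry requires active deterioration and these patients have just finished steroids, so hearing may fall further before the first dose. The old reading would then be too good and would hide benefit. The 30-day allowance is also written only for referred patients; the ordinary route identifies the patient at the end of the steroid course.

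Sections 5.3 and 6.1 need not contradict each other, since 6.1 can be read as naming which audiogram fills the day-0 slot. That reading leaves the reuse in place.

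Section 6.1 blinds the audiologists to timepoint. This guards against biased testing, but not against a chance error already fixed by the selection.

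**Conclusion.** The point holds as a modest design weakness. The same reading selects patients for not improving and then serves as the reference for improvement, so with an inert drug and no drift the expected change favours anakinra under every assumption examined. The section 7.1 argument fails for the same reason.

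With stable hearing, reuse adds 0.2 to 3.5 percentage points of false response for SDs from 2 to 4 dB. With the assumed variable steroid change it adds 1.1 to 6.2 points (for example 15.6% against 11.9% at 3 dB). It is negligible to small at 2 dB and matters from about 2.5 to 3 dB upwards.

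These sizes rest on an assumed SD, independent normal errors, one ear, PTA only (speech discrimination is ignored on both sides) and the derived cut-off of more than 5 of 29. The direction of the selection effect does not depend on the values chosen.

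The missing age limit is a separate, smaller gap. It adds uncertainty of unknown sign and cannot be counted as bias towards improvement.

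**What to change.** In section 6.1, use the end-of-steroid audiogram for eligibility only. Take the day-0 audiogram that section 5.3 already lists at Visit 1, before the first dose, and make it the baseline for PTA change, with no role in eligibility. Reword sections 5.3 and 6.1 so that both name this test as time 0. Testing at Visit 1 also settles the age of the baseline. In section 7.1, delete the argument that no placebo effect is expected because of the two earlier audiograms.

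The cost is protocol wording, at most one extra non-invasive audiogram per patient at an existing visit, and slightly fewer responses. The change removes the selection effect. It does not remove false responses from ordinary measurement error around the 5 dB cut-off.

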4.2 Exclusion Criteria

- 1. Patients over 75 years of age, because there is a higher incidence of infections in the elderly population in general, caution should be used in treating the elderly.
- 2. Patients with evidence of retrocochlear pathology (vestibular schwannoma) or inner ear malformation (Mondini Malformation or Enlarged Vestibular Aqueduct) based on imaging.
- 3. Patients concurrently receiving methotrexate or TNF-antagonist therapy.
- 4. Patients with a diagnosis of any immunodeficiency syndrome.
- 5. Patients with active or chronic infections.
- 6. Patients currently receiving, or having received treatment for a malignancy in the past three years.
- 7. Patients that developed an immediate onset, profound SNHL with 0% speech discrimination scores.
- 8. Patients whose hearing loss coincided with significant, disabling episodes of vertigo.
- 9. Patients with a diagnosis of chronic renal insufficiency (a creatinine clearance of <49mL/min) or chronic renal failure.
- 10. Patients with evidence of neutropenia (an ANC of < 1000) prior to treatment with Anakinra.
- 11. Patients with known hypersensitivity to E. coli derived products.
- 12. Patients with latex sensitivity (the needle cover is a derivative of latex).
- 13. Pregnant or lactating females.
- 14. Children under the age of 13, as Anakinra is supplied in pre-filled syringes dosed for adult sized patients..
- 15. Non-English speaking patients, as the word recognition scoring is in English and is a vital component to the efficacy analysis.

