6.5 Visit 5 (Follow-up period)

At 30 days following the discontinuation of treatment, enrolled patients will return for an audiometric evaluation and blood collection. If any patient develops a new decline in hearing during the 180 day follow-up period, standard corticosteroid therapy or retreatment with anakinra will be offered. The blood specimen would be used to determine the CBC with differential, SMA-7, and IL-1 β plasma level and induction. If retreatment with anakinra is indicated, a beta HCG will also be obtained (if female) before patient resumes study medication and daily symptom logs will be restarted. A 28 day dose box of anakinra will be given free of charge to the patient if retreatment is indicated during the 180 day follow up period. At that point, a letter may be sent to the patient's insurance company for possible coverage of the drug in case a sustained use of anakinra is necessary. During the 180 follow up period, the maximum number of times a patient can receive a 28 day dose of anakinra would be 4, however, we may not be able to provide this medication free of charge for this duration.

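### Pregnancy blocks the first anakinra dose, but at days 28 and 56 the next box is dispensed with no HCG condition, HCG has no review time, and no on-treatment stop list names pregnancy

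*Protocol*

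**What the plan says.** **Entry and first dose.** Protocol 4.2 item 13 excludes "Pregnant or lactating females". In 6.1 the Visit 1 laboratory results act as a gate: "if there is no evidence of neutropenia, renal insufficiency or pregnancy, the patient will be asked to meet with study nurses" for injection training. Pregnancy is one of the three conditions.

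**Days 28 and 56.** Section 6.2 orders a serum HCG for females of child-bearing age at Visit 2. For Visit 3, section 6.3 says "The blood specimen would be used to determine the CBC with differential, SMA-7, beta HCG" along with IL-1β. In both sections:

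- dispensing is unconditional: "The patient would be given a new 28 day supply of Anakinra and a new sharps container";
- the review deadline is limited to two tests: "CBC and SMA-7 results would be reviewed within 72 hours";
- the contact trigger is limited to three values: "any patients with changes in their white blood cell numbers, neutrophils numbers or creatinine values will be contacted";
- the stop sentence names two conditions: "Any patient that develops neutropenia or renal insufficiency will be excluded from receiving further drug".

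**General stop lists.** Section 4.4.1 gives six indications for ending anakinra early: neutropenia, serious bacterial infection, severe injection site reaction, allergic rash, PTA worsening of more than 20 dB, and renal insufficiency. Section 8.5 gives the same six in substance and cites 4.4.1. Pregnancy is in neither.

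**Retreatment.** For drug restarted in follow-up, 6.5 ties the test to dosing: "a beta HCG will also be obtained (if female) before patient resumes study medication".

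**Other pregnancy text.** Section 3.1 includes HCG or UCG in the 28-day laboratory monitoring. Section 11.2 says the risk to an unborn baby is not well known, that pregnant women should not take part, and that contraception is needed throughout treatment.

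**The concern.** The protocol treats pregnancy as a bar to the drug and repeats the test during treatment, but attaches nothing to the repeat result. In the same paragraphs the other two laboratory safety conditions get a reading deadline, a contact rule and a stop. The three-part gate of 6.1 becomes a two-part rule in 6.2 and 6.3.

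This matters in practice because 8.5 says the study nurses and the DSMB will be told of its stopping rules, and a nurse dispenses the boxes (5.4). Someone working from those sections would not learn when to look at an on-treatment HCG, or what to do if it is positive. At stake is fetal exposure that a prompt reading would prevent. These are conduct rules, which belong in the protocol and not in a statistical analysis plan.

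**Working it through.** The protocol states no figure on this point, so the check compares the texts and then counts doses.

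**1. The three laboratory conditions, place by place**

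| Place | Neutropenia | Renal insufficiency | Pregnancy |
|---|---|---|---|
| 6.1, before first dose | blocks | blocks | blocks |
| 6.2 and 6.3, test drawn | yes (CBC) | yes (SMA-7) | yes (HCG) |
| 6.2 and 6.3, read within 72 hours | yes | yes | not stated |
| 6.2 and 6.3, contact trigger | yes | yes (creatinine) | not stated |
| 6.2 and 6.3, no further drug | yes | yes | not stated |
| 4.4.1 and 8.5, stop list | yes | yes | not stated |
| 6.5, test before retreatment | CBC drawn | SMA-7 drawn | HCG before drug resumes |

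**2. Counting the stop conditions.** Sections 4.4.1 and 8.5 contain six distinct conditions between them. The two in 6.2 and 6.3 are among those six. Pregnancy is in 0 of 6.

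**3. Doses that could follow a positive sample, read literally.** Inputs: 84 daily doses (5.2), boxes of 28 (5.1), HCG at days 28 and 56 (6.2, 6.3).

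- Positive at day 28: 84 − 28 = 56 doses remain. Visit 3 has the same gap, so nothing written at day 56 changes this.
- Positive at day 56: 84 − 56 = 28 doses remain.

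**4. The same count under a written rule**

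- Negative urine test required before the box is handed over: 0 doses after a positive sample.
- HCG in the 72-hour review, assuming contact and stop on the day of review: about 3 doses (72 hours ÷ 24 hours), or 3/28 = 11% of one box.

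With no HCG rule, a pregnancy might still come up at the weekly nurse contact (5.5), about every 7 doses. That contact concerns injection times and reactions and is not tied to HCG.

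**5. Room for a lost patient.** Planned enrolment is 38 for 29 evaluable (7.1), so 38 − 29 = 9 places are spare.

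**The case against.** The strongest reply is that the rule already exists in substance. Section 11.2 says pregnant women should not be in the study and requires contraception throughout treatment, so it covers more than entry. Section 3.1 puts the test into 28-day monitoring, and 8.6 makes the Principal Investigator responsible for safety. A serial pregnancy test in a trial that bars pregnancy has one plausible purpose. This stands, and it limits the point to timing and explicit action.

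The stop lists are also not exhaustive. Section 5.5 withdraws most patients after an unsanctioned lapse of more than 72 hours, and neither 4.4.1 nor 8.5 lists that. A reader might infer from the omission that the protocol keeps a pregnant woman on drug. The documents do not support that: absence from these lists does not mean treatment continues, and 11.2 points the other way.

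Two contrasts are weaker than they look. Dispensing before results applies to CBC and SMA-7 as well. And 6.5 orders the HCG before retreatment without saying what follows if it is positive. Both are fair. But for CBC and SMA-7 a 72-hour limit and, for the two named conditions, a stop close the interval after dispensing. For HCG nothing does. Section 6.5 at least places the test before the drug.

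None of this text gives a time by which the day-28 or day-56 HCG must be read.

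**Conclusion.** The point holds as a minor participant-safety gap. During the 84-day course no text makes dispensing depend on HCG, sets a time for reading it, or states a stop if it is positive.

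The bounds of 56 and 28 doses are literal-reading limits, not forecasts; 11.2 and 8.6 make an earlier stop likely. A reader might also treat boxes 2 and 3, which are 56 of 84 doses (67%), as the size of the harm. That figure is only the share of the schedule dispensed at Visits 2 and 3 to every patient, including men. The exposed group is women who conceive despite required contraception. The protocol does not give the number of women of child-bearing age among the roughly 38 enrolled, so no frequency can be derived.

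The omission is certain from the text; its practical consequence is not. The primary endpoint, the Simon two-stage figures and the error rates are unaffected. Nor does this point show that the study-wide safety stop in 8.5 needs changing. Whether a pregnancy withdrawal should count toward it is a separate judgement.

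**What to change.** - **Visits 2 and 3 (preferred).** Require a negative urine HCG before the next box is handed to a woman of child-bearing age. Section 3.1 already permits UCG in the 28-day monitoring, so 6.2 and 6.3 need only allow it.
- **Minimum alternative.** Add HCG to the results reviewed within 72 hours in 6.2 and 6.3, with contact and stop if positive.
- **In either case.** Repeat the three conditions of 6.1 in the stop sentences of 6.2 and 6.3, and add pregnancy to the lists in 4.4.1 and 8.5.

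The cost is wording, plus at most two urine tests per woman of child-bearing age if the dispensing check is chosen. An occasional patient may become non-evaluable, which the 9 spare places should absorb.
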